6. OBJECTIVES

PRIMARY OBJECTIVE

Fatigue-related quality of life of patients receiving a tyrosine kinase inhibitor evaluated using the validated 13-item FACIT-Fatigue scale for patients with metastatic renal cancer in Spanish.^{1,2}

SECONDARY OBJECTIVES

- 1) Quality of life in patients with palmar-plantar erythrodysaesthesia (hand-foot syndrome).
- 2) To assess the following adverse effects according to version 4 of the CTCAE (Common Terminology Criteria for Adverse Events): any grade of fatigue and HFS.
- 3) To study what role aerobic exercise (walking quickly, running, swimming, playing tennis, dancing and/or riding a bike) plays in the onset of fatigue before starting and during treatment.
- 4) To evaluate what impact the time of drug administration, napping, off-treatment periods, temporary treatment breaks and dose reductions have on controlling fatigue and hand-foot syndrome.
- 5) Time to Treatment Failure (TTF), defined as the time from the start of treatment with a tyrosine kinase inhibitor to tumour progression, treatment discontinuation for any reason or death from any cause.
- 6) Progression-Free Survival (PFS) (median): time from the start of treatment with a tyrosine kinase inhibitor to tumour progression or death from any cause.
- 7) Objective Response Rate according to RECIST version 1.1.

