#### SECONDARY OBJECTIVES

- 1) Quality of life in patients with palmar-plantar erythrodysaesthesia (hand-foot syndrome).
- 2) To assess the following adverse events according to version 4 of the CTCAE (Common Terminology Criteria for Adverse Events): any grade of fatigue and HFS.
- 3) To study what role aerobic exercise (walking quickly, running, swimming, playing tennis, dancing and/or riding a bike) plays in the onset of fatigue before starting and during treatment.
- 4) To evaluate what impact the time of day of drug administration, napping, temporary treatment breaks and dose reductions have on controlling fatigue and hand-foot syndrome.
- 5) Time to Treatment Failure (TTF), defined as the time from the start of treatment with a tyrosine kinase inhibitor to tumour progression, treatment discontinuation for any reason or death from any cause.
- 6) Progression-Free Survival (PFS) (median): time from the start of treatment with a tyrosine kinase inhibitor to tumour progression or death from any cause.
- 7) Objective Response Rate according to RECIST version 1.1.

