#### TREATMENT

- 1) Time when the oral treatment is taken
- 2) Tyrosine kinase inhibitor dose and treatment regimen
- 3) Number of dose changes per treatment cycle
- 4) Temporary treatment interruptions, number of interruptions per treatment cycle
- 5) Best response achieved with first-line treatment
- 6) Mean duration of treatment
- 7) Time to treatment failure
- 8) How long each patient stays on first-line treatment/no. of cycles received
- 9) Reason for discontinuing the first-line drug
- 10) Date of disease progression and/or death

Through the analysis of the collected variables the following aspects will be assessed:

- **Progression-Free Survival (PFS):** defined as the interval from the start of treatment to the date of the first documentation of objective tumour progression or death from any cause.

- **Objective Response Rate (ORR):** Defined as the proportion of subjects who achieve complete remission (CR) or partial response (PR). In addition, subjects with stable disease (SD) will also be evaluated to obtain clinical benefit along with subjects with tumour progression. Subjects will be evaluated according to RECIST 1.1.

- **Duration of response (DOR):** in patients with PR or CR, it will be defined as the interval from the date the response is documented to the first date that progressive disease is observed.

- **Safety:** The safety of the tyrosine kinase inhibitor will be evaluated describing the incidence and all grades in the event of fatigue and or hand-foot syndrome.

- **Fatigue-related quality of life of patients:** this will be measured based on the results obtained after completion of the FACIT-Fatigue questionnaire by the patient.

- **HFS-related quality of life of patients** in cases in which HFS is present with a score from 1 to 3 according to version 4 of the CTCAE (Common Terminology Criteria for Adverse Events).

- Date of disease progression and/or death.

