#### 6.1 EFFICACY/EFFECTIVENESS OBJECTIVES

- Progression-Free Survival (PFS): PFS will be studied using Kaplan Maier survival curves, considering progression/death as the event and time to event as the interval from the start of treatment until the first date that progressive disease (PD) is observed according to RECIST criteria (Version 1.1) or until *death*. Patients who have not had an event at the time of the analysis of the study data will be censored on the date of the last available follow-up.

- Objective Response Rate (ORR): defined as the proportion of subjects who achieve complete remission (CR) or partial response (PR). Additionally, the patients with stable disease (SD) will be evaluated. The subjects will be evaluated in accordance with RECIST criteria (Version 1.1).

- Duration of response (DOR): in patients with PR or CR, it will be defined as the interval from the date the response is documented to the first date that progressive disease is observed.

\_Time to Treatment Failure (TTF), defined as the time from the start of treatment with a tyrosine kinase inhibitor to tumour progression, treatment discontinuation for any reason or death from any cause.

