#### 8 STATISTICAL ANALYSIS AND METHODOLOGY

#### 8.1 STATISTICAL METHODS

The investigator will collect data from the enrolled patients in an electronic Case Report Form specially designed for this study.

The patient number we provide is a serial number devoid of any identifying value.

The information is stored in an Access database, which in turn is associated with a file, "WorkGroup", detailing the user code and permits of the investigator within the database. People not within this working group cannot access the database.

A Data Management Plan (DMP) will be developed and once approved by the person responsible for the study, the "Queries" will be programmed in the electronic case form so that when the investigator saves the data, it informs him/her of any doubts regarding the data.

All changes made by the investigators during the collection of data will be stored in a table specially designed for this purpose, indicating the user, date, modified field, the old value and the new value.

The fatigue-related quality of life of the patients and the quality of life of patients with palmar-plantar erythrodysaesthesia (hand-foot syndrome) will be studied using the mean, standard deviation and confidence intervals if they follow normal distribution, or the median, minimum, maximum and interquartile range if they do not follow Gaussian distribution. The Wilcoxon test will be used to analyse the inter-visit correlation for patients' quality of life.

The objective response rate according to RECIST version 1.1 will be studied using absolute and relative frequencies.

In order to study the impact of drug administration time, napping, temporary interruptions and dose reductions on fatigue and hand-foot syndrome control, independent samples will be compared using Pearson's chi-square test (or Fisher's exact test for 2x2 tables or likelihood ratio test for mxm tables, if necessary) in the case of qualitative variables and Student's t-test, one-way ANOVA test or non-parametric equivalents, such as the Mann-Whitney U test or Kruskal-Wallis H test in the case of quantitative variables.

The Kaplan-Meier survival estimate will be used to study both the PFS and TTF of patients. The log-rank test will be used to compare the survival distributions.

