## • Has taken the medication:

- In the morning (between 7 am and 12 noon)
- In the afternoon (between 1 pm and 7 pm)
- At night (between 8 pm and 6 am)
- I have not taken any medication this week

For each one of the weekly habits described above, a summary calculation will be made (after three months) of each patient's habits in terms of daytime rest, physical exercise and taking their medication, taking the options marked with greater frequency in the last 12 weeks into account.

FACIT\_Fatigue: The main measures of centrality and dispersion measures will be calculated (mean, standard deviation, median, minimum, maximum, IR and 95%CI ) from the score obtained in the FACIT\_Fatigue quality of life scale, calculated as described in ANNEX 1. The absolute and relative frequency of patients with severe fatigue, being those with a score of less than 30 points on the FACIT\_Fatigue scale, will also be presented.

For each one of the evolution visits (week 6, week 12, week 18, week 24, week 30 and week 36), a study will be performed to ascertain whether significant changes have occurred in fatigue-related quality of life versus the previous evaluation, and defined as:

- **Improvement:** if there is an increase of more than 4 points in the FACIT\_Fatigue scale score versus the previous evaluation
- **Maintenance:** if the score on the quality of life scale does not vary by more than 4 points versus the previous evaluation
- **Worsening:** if the score obtained on the Facit\_Fatigue scale decreases by more than four points versus the previous evaluation.

Significant associations will be sought between the habits of daytime rest, the practice of physical aerobic exercise, medication taken, dose and treatment schedule changes, dose interruptions and the number of days of treatment

interruption depending on the evolution in the evaluation of the fatigue in the FACIT\_Fatigue over the last six weeks. The Pearson chi-squared test will be used for this purpose (or Fisher's exact test for 2x2 tables or likelihood ratio test for mxn tables, if necessary).

- Treatment: For each one of the treatment cycles received by patients during the 9-month follow-up, the following will be studied:
  - **Dose change:** the absolute and relative frequency of patients who have changed doses since the last cycle will be provided. In the sub-population of patients with dose changes in the last cycle, their frequency distribution will be presented according to:

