    - Number of dose changes received
      - 1 change \_ New dose
        - Sunitinib 50 mg 4/2 regimen
        - Sunitinib 50 mg 2/1 regimen
        - Sunitinib 37.5 mg 4/2 regimen
        - Sunitinib 37.5 mg 2/1 regimen
        - Sunitinib 25 mg 4/2 regimen
        - Sunitinib 25 mg 2/1 regimen
        - Pazopanib 800 mg/24 hours continuous
        - Pazopanib 400 mg/24 hours continuous
        - Sorafenib 400 mg/24 hours continuous
        - Sorafenib 400 mg/12 hours continuous
      - 2 changes\_ New dose
        - Sunitinib 50 mg 4/2 regimen
        - Sunitinib 50 mg 2/1 regimen
        - Sunitinib 37.5 mg 4/2 regimen
        - Sunitinib 37.5 mg 2/1 regimen
        - Sunitinib 25 mg 4/2 regimen
        - Sunitinib 25 mg 2/1 regimen
        - Pazopanib 800 mg/24 hours continuous
        - Pazopanib 400 mg/24 hours continuous
        - Sorafenib 400 mg/24 hours continuous
        - Sorafenib 400 mg/12 hours continuous
  - **Treatment interruptions:** the absolute and relative frequency of patients who have interrupted the treatment since the last cycle will be given. In

the sub-population of patients with treatment interruptions, their frequency distribution will be presented according to:

- Number of treatment interruptions
  - 1
  - 2
  - 3
  - 4 •
  - 5 •
  - ...
- Total calculation of days of treatment interruption
  - <7 days
  - 7-14 days
  - >14 days

In order to study the evolution of patients in terms of the presence of AEs (HFS and fatigue), patient habits in terms of daytime rest, aerobic physical exercise and taking medication, paired data comparisons will be performed between each one of the visits with the results of the previous visit, as well as of each one of the visits with regard to the results presented at the baseline visit, using, for this purpose, the non-parametric sign tests for categorical variables or the McNemar test in the case of dichotomous variables. In order to ascertain whether there is a significant evolution in the score obtained on the FACIT Fatigue scale throughout the study, comparisons of paired data will be performed for each one of the assessments with regard to the baseline value and with regard to the

previous evaluation using the Student t-test for paired data or the non-parametric Wilcoxon test, as appropriate.

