#### 9 LIST OF TABLES AND TABLE OF CONTENTS

Table/Graph number			Table/Graph title					
1.			Included and evaluable population					
2.			Descriptive analysis					
	.1		Demographic and disease information					
		.1	Age					
		.2	Time from diagnosis and from the advanced diagnosis of the disease					
		.3	Gender					
		.4	ECOG at time of diagnosis, Heng prognostic criteria and site of metastasis					
		.5	Histological type					
		.6	Smoking					
	.2		Dosage and treatment regimen of tyrosine kinase with which the patient begins treatment					
3.			Analysis of evolution					
	.1		Presence of palmar-plantar erythrodysesthesia of any grade (month 3, month 6, month 9)					
		.1	Association between medication intake habits and evolution of hand- foot syndrome (every three months)					
		.2	Association between dose changes and evolution of hand-foot syndrome (every three months)					
		.3	Association between dose, treatment regimen received and the evolution of hand-foot syndrome (every three months)					
		.4	Association between temporary treatment interruptions and evolution of hand-foot syndrome (every three months)					
	.2		Presence of fatigue of any grade (baseline, month 3, month 6, month 9)					
		.1	Association between daytime rest habit and fatigue evolution (every three months)					
		.2	Association between daytime physical exercise and fatigue evolution (every three months)					
		.3	Association between daytime medication-taking habits and fatigue evolution (every three months)					
		.4	Association between daytime dose changes and fatigue evolution (every three months)					
		.5	Association between doses, daytime treatment regimen and fatigue evolution (every three months)					

CT24-GSOP-SD-GL04 NI Study SAP Template; Template Version 1.0, Effective 31-Dec-2013 Page 23 of 29

PFIZER CONFIDENTIAL

	.6	Association between temporary daytime interruptions and fatigue evolution (every three months)
	3	Data from the patient diary
	.1	Daytime rest (weekly)
	.2	Physical exercise (weekly)
	.3	Has taken the medication (weekly)
•-	4	Quality of life (FACIT_Fatigue) (every six weeks)
	.1	Association between daytime habit and evolution on the Facit_Fatigue (every six weeks)
	.2	Association between daytime physical exercise and evolution on the Facit_Fatigue (every six weeks)
	.3	Association between daytime medication-taking habits and evolution on the Facit_Fatigue (every six weeks)

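### Objective 4 asks about dose reductions, but the SAP's association tables use undirected dose changes and no rule derives a reduction

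*SAP*

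**What the plan says.** **Where reductions are named.** Objective 4 in Protocol Section 6 asks what impact several factors, including "temporary treatment breaks and dose reductions have on controlling fatigue and hand-foot syndrome". The SAP's secondary objectives (Section 2.2) keep this factor. SAP Section 8.1 carries it into the methods: for "temporary interruptions and dose reductions on fatigue and hand-foot syndrome control, independent samples will be compared using" Pearson's chi-square test or the listed alternatives. Protocol Section 7.2 and SAP Section 2.1 add that reductions are recorded on the CRF at each visit.

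**Where the analysis is specified.**
- The treatment variables in SAP Section 6 include "Number of dose changes per treatment cycle", with no direction.
- The treatment part of SAP Section 8.2.3 says that "the absolute and relative frequency of patients who have changed doses since the last cycle will be provided". Patients with a change are then broken down by "Number of dose changes received" and, for a first and a second change, by the new regimen. That list has ten entries: six for sunitinib (three doses, each on 4/2 and 2/1), two for pazopanib and two for sorafenib. The regimen before the change is not shown.
- The association text in Section 8.2.3, for CTCAE fatigue and for FACIT-Fatigue, names changes of dose and of schedule together as factors. The HFS text there names no association factors.
- In Section 9, Table 3.1.2 is titled "Association between dose changes and evolution of hand-foot syndrome (every three months"). Tables 3.2.4 and 3.4.4 do the same for CTCAE fatigue and FACIT-Fatigue. Tables 3.1.3, 3.2.5 and 3.4.5 concern the dose and regimen received, which is a level and not a change.

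**The concern.** A reduction, a re-escalation and a move between 4/2 and 2/1 at the same dose are different exposures. Reductions and increases would be expected to move fatigue and HFS in opposite directions. The background sections describe 2/1 as a way to improve tolerability while keeping dose intensity, which is a different measure from lowering the dose. If all of these enter one dose-change factor, the result does not answer the question in objective 4, and a real association with reductions may be diluted. If direction is left undefined until the data are seen, the choice of definition becomes post hoc.

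**Working it through.** The plan states no figure on this point, so there is none to reproduce. The check has three steps.

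**1. What the ten listed regimens allow.** Inputs: the regimen lists in SAP Sections 8.2.2 and 8.2.3. Ordered changes: 10 × 9 = 90.

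| Type | Count | Derivation |
|---|---|---|
| Same-drug reduction | 14 | sunitinib 3 dose pairs × 2 × 2 schedules = 12, pazopanib 1, sorafenib 1 |
| Same-drug increase | 14 | mirror image |
| Schedule only, same dose | 6 | 3 sunitinib doses × 2 directions |
| Different TKI | 56 | 90 − 34 |

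Within one drug, 14/34 = 41% of the possible changes are reductions. These are possibilities, not expected frequencies.

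What the new regimen alone reveals, within one drug:
- Sunitinib 37.5 mg: reduction, increase or schedule switch.
- Sunitinib 25 mg: reduction or schedule switch.
- Sunitinib 50 mg: increase or schedule switch, never a reduction.
- Pazopanib 400 mg and sorafenib 400 mg/24 h: reduction only.
- Pazopanib 800 mg and sorafenib 400 mg/12 h: increase only.

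The ambiguity therefore lies in sunitinib, which both documents call the most widely used targeted agent.

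**2. Whether a schedule switch lowers exposure.** Average daily dose = dose × days on / cycle length. For 50 mg on 4/2: 50 × 28/42 = 33.3 mg/day. For 50 mg on 2/1: 50 × 14/21 = 33.3 mg/day. A move between them appears as a new dose but is not a reduction. Both schedules are two-thirds on treatment, so ranking sunitinib changes by daily dose or by average dose gives the same direction.

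**3. How much dilution could follow.** The documents give reduction rates from earlier studies (50% in the pivotal sunitinib trial, 30% in expanded access) but no rates of re-escalation, schedule switch or improvement. The figures below rest on assumptions and show only the mechanism.

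*Other changes behave like no change.* Assume 50% improve after a reduction and 25% otherwise, with 95 patients (100 less the 5% discontinuation in SAP Section 5.1) and a two-sided 5% test. If reductions are a share s of all changes, the observed difference is s × 25 points.

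| s | Difference (points) | Power, 47 changed v 48 not | Power, 30 v 65 |
|---|---|---|---|
| 100% | 25 | 72% | 67% |
| 75% | 18.8 | 49% | 45% |
| 50% | 12.5 | 26% | 25% |
| 25% | 6.3 | 10% | 10% |

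*Other changes also differ.* Assume improvement in 60% after a reduction, 35% after a schedule switch, 15% after a re-escalation and 40% with no change. The undiluted difference is 60 − 40 = 20 points.
- 25 reductions, 10 schedule switches, 15 re-escalations: (25×0.60 + 10×0.35 + 15×0.15)/50 = 20.75/50 = 41.5%, a difference of 1.5 points.
- 40, 5 and 5: (40×0.60 + 5×0.35 + 5×0.15)/50 = 26.5/50 = 53%, a difference of 13 points.

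The unknown mix alone moves the answer from 1.5 to 13 points.

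**The case against.** The strongest reply is that this is a mismatch of wording. SAP Sections 2.1 and 8.1 name reductions, the CRF records them, and dose change may be shorthand for a CRF item; the CRF was not available for this review. The tests are also not fixed as changed versus unchanged: Section 8.2.3 allows larger tables with a likelihood-ratio test. Schedule changes are of legitimate interest, since protocol objective 4 also lists off-treatment periods and the SAP names schedule changes openly. Direction can be read for pazopanib and sorafenib. Finer classes would give sparse cells with about 95 patients.

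Most of this stands and limits the point:
- A reader might infer that the SAP plans to analyse only any change. Section 8.1 contradicts that; the fault is an internal inconsistency with a missing derivation.
- A reader might infer that all changes are certain to be coded as one yes/no group. The coding is unspecified, so the tables can mix the classes, but that they will is not established.
- A reader might infer that a switch to another TKI counts as a dose change and so clashes with time to treatment failure, which ends at "treatment discontinuation for any reason or death from any cause". The shared regimen list does not say so; the SAP neither includes nor excludes such switches.

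What the reply does not remove is that no planned association table names reduction as its exposure and no rule defines one. For HFS, the titles in Section 9 are the only specific plan. Interest in schedule changes is a reason to show them separately.

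**Conclusion.** The concern holds in a limited form. Objective 4 and SAP Section 8.1 ask about reductions; the association text in Section 8.2.3 and Tables 3.1.2, 3.2.4 and 3.4.4 use undirected changes, and the breakdown omits the previous regimen. Run as written, those tables do not isolate reductions and may dilute their association with fatigue and HFS.

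The size cannot be given from the documents. A reader might infer that the association would all but vanish or reverse. The 1.5-point result needs an assumed high share of re-escalations, another assumed mix leaves 13 points, and no example here shows a reversal. A reader might also infer that the effect of reductions cannot be recovered at all. That goes too far: the starting regimen and each new regimen are planned items, so direction can be derived, assuming the database keeps them in sequence. Severity is minor to moderate: one factor of one secondary objective in a study that calls itself descriptive.

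**What to change.** Before the analysis, amend the SAP as follows:
1. In Section 8.2.3, derive the direction of each change from the recorded previous and new regimens within the same TKI: reduction, increase, or schedule change at the same daily dose.
2. In Tables 3.1.2, 3.2.4 and 3.4.4, use reduction since the previous evaluation (yes/no) as the exposure for objective 4. State the window for each table: three months for HFS and CTCAE fatigue, six weeks for FACIT-Fatigue.
3. Report increases and schedule-only changes descriptively, as separate classes. This keeps the main comparison at two levels and limits sparse cells.
4. State a rule for windows that hold both a reduction and an increase, for example a separate mixed class.
5. State whether TKI switches are excluded from dose change, consistently with the definition of time to treatment failure in Section 6.1.
6. Align the wording of Sections 8.1, 8.2.3 and 9.

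The cost is a derivation rule and smaller cells. No new data are needed.

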## 4 HYPOTHESIS TESTING

The statistical significance value is set to p<0.05 The SPSS statistical package, V19.0 or later will be used.

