## 8.2.3 Follow-up analysis

The evolution of the following aspects will be presented for each one of the follow-up visits of the patients at which the variables listed below are recorded:

- Presence of palmar-plantar erythrodysesthesia: the absolute and relative frequency of patients who as of month 3 of treatment develop palmar-plantar erythrodysesthesia of any grade will be provided. In the sub-population of patients with hand-foot syndrome, the frequency distribution will be presented according to the degree of severity of these AE, according to CTCAE (Common Terminology Criteria form Adverse Event) version 4:
  - o Grade 1
  - o Grade 2

#### o Grade 3

For each one of the evolution visits (month 6 and month 9), a study will be performed to ascertain whether significant changes have occurred in the presence and the grade of the HFS with regard to the previous visit, defined as (improved, maintained or worsened). The Pearson chi-squared test will be used for this purpose (or Fisher's exact test for 2x2 tables or likelihood ratio test for mxn tables, if necessary).

- Presence of fatigue: the absolute and relative frequency of patients with the presence of fatigue of any degree since the baseline visit will be provided. In the sub-population of patients with fatigue, the frequency distribution will be presented according to the degree of severity, according to CTCAE (Common Terminology Criteria form Adverse Event) version 4:
  - o Grade 1
  - o Grade 2
  - o Grade 3
  - o Grade 4

For each one of the evolution visits (month 3, month 6 and month 9), a study will be performed to ascertain whether significant changes have occurred in the grade of fatigue with regard to the previous visit, defined as (improved, maintained or worsened). Significant associations will be sought between the habits of daytime rest, physical aerobic exercise, medication taken, dose and treatment schedule changes, dose interruptions and the number of days of treatment interruption depending on the evolution of the presence and degree of fatigue in the last twelve weeks. The Pearson Chi-squared test will be used for this purpose (or Fisher's exact test for 2x2 tables or likelihood ratio test for mxn tables, if necessary).

- Patient diary data (weekly): the distribution of patient frequencies will be presented according to the following habits:
  - Napping
    - Every day
    - Weekend and/or holidays
    - Sporadically, between 2 or 6 days
    - Has not taken a nap any day

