#### • Physical exercise:

- I have not done any kind of physical exercise
- I have done at least 45 minutes of physical exercise 2-3 days a week
- I have done 45 min of physical exercise 4-5 days a week for at least 6 months
- I have done at least 45 minutes of physical exercise every day

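### The SAP's paired sign test is undefined for medication time and for the middle napping options, and its baseline tests of HFS and medication time are uninformative

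*SAP*

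**What the plan says.** The closing paragraph of SAP 8.2.3 covers change over time in "the presence of AEs (HFS and fatigue), patient habits in terms of daytime rest, aerobic physical exercise and taking medication". Each visit is compared with the previous one, and the paragraph adds a second comparator: "as well as of each one of the visits with regard to the results presented at the baseline visit". One clause then names the tests for all of these variables together: "using, for this purpose, the non-parametric sign tests for categorical variables or the McNemar test in the case of dichotomous variables". The paragraph does not assign tests to individual variables and gives no category order.

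The categories are set out earlier in 8.2.3:

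- Medication time has four options. The first is "In the morning (between 7 am and 12 noon"), followed by afternoon, night, and no medication that week.
- Napping runs from every day to never. Between these lie weekends and/or holidays, and "Sporadically, between 2 or 6 days".
- Exercise runs from none, through options such as "I have done at least 45 minutes of physical exercise 2-3 days a week", to every day.
- HFS and fatigue are given as presence and as CTCAE grade. HFS is reported for "patients who as of month 3 of treatment develop palmar-plantar erythrodysesthesia of any grade".

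The table list in SAP section 9 gives HFS at months 3, 6 and 9, but gives fatigue at baseline as well. SAP 2.1 places baseline before the start of treatment. SAP section 4 sets the threshold: "The statistical significance value is set to p<0.05".

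**The concern.** A sign test counts upward and downward moves and asks whether they are equally likely. If the categories have no order, up and down are fixed only by the numbers the programmer assigns, and two programmers following the same SAP can reach opposite conclusions. McNemar does not help, because these variables have more than two levels.

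The baseline comparison raises a different difficulty. A patient who has not started the drug has no time of taking it, and the SAP presents no HFS before month 3. Either the test has no pairs, or baseline is set to absent for everyone and the test only confirms that something occurred after treatment began.

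At stake are statements of significant or non-significant change in medication timing, napping and HFS that would reflect coding or a structural zero.

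**Working it through.** The documents give no p-value, power or sample size for these tests, so there is no stated figure to reproduce. The tables below are hypothetical.

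**Inputs.** Alpha is 0.05 (SAP section 4); sidedness is not stated, so two-sided is assumed. SAP 5.1 plans 100 patients with 5% discontinuation, which gives at most 100 × 0.95 = 95 pairs. The sign test is the exact binomial test on discordant pairs with probability 0.5.

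**1. Medication time, moderate example.** Of 95 patients, 65 do not change. The moves are morning to night 14, night to morning 4, morning to afternoon 3, afternoon to morning 5, afternoon to night 2, night to afternoon 2.

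- Order morning < afternoon < night: up 14 + 3 + 2 = 19, down 4 + 5 + 2 = 11, p = 0.200.
- Order afternoon < morning < night: up 14 + 5 + 2 = 21, down 4 + 3 + 2 = 9, p = 0.043.
- Bowker, which needs no order: (14 − 4)²/18 + (3 − 5)²/8 + (2 − 2)²/4 = 5.56 + 0.50 + 0 = 6.06 on 3 df, p = 0.109.
- Stuart-Maxwell: 4.55 on 2 df, p = 0.103, whatever the order.

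**2. Medication time, extreme example.** Twelve patients move from morning to night and twelve from night to afternoon.

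- Order morning < afternoon < night: 12 v 12, p = 1.0.
- Order morning < night < afternoon: 24 v 0, p = 2 × 0.5²⁴ = 1.2 × 10⁻⁷.
- Stuart-Maxwell: 12²/12 + 12²/12 = 24 on 2 df, p about 6 × 10⁻⁶. There is a real marginal shift (12 fewer in the morning, 12 more in the afternoon), and the clock order misses it.

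**3. Napping.** In a hypothetical table of 95 pairs, 9 patients move from weekend to sporadic and 2 move back.

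- Sporadic ranked above weekend: 26 v 13, p = 0.053.
- The two middle options swapped: up 26 − 9 + 2 = 19, down 13 − 2 + 9 = 20, p = 1.00.

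**4. Exercise, as a control.** The options are ordered by frequency. A hypothetical table gives 11 v 26, p = 0.020, and reversing the order gives 26 v 11 with the same p. No arbitrary coding enters.

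**5. HFS against an all-absent baseline.** With b patients having HFS at the later visit, every discordant pair points the same way, so exact McNemar gives p = 2 × 0.5ᵇ.

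- b = 5: p = 0.0625. b = 6: p = 0.031. The threshold is 6/95 = 6.3% of patients.
- Chance that b is at least 6 among 95 pairs, by assumed HFS rate at the visit: 87% at 9%, 92% at 10%, above 99.9% at 20%. With 60 pairs: 46%, 56% and 98.8%.

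The result therefore tracks the HFS rate and the number of pairs, both of which a simple incidence shows directly.

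**6. Medication time against baseline.** If baseline is coded as not taken and that category sits at one end of the order, every patient on drug moves the same way. The formula in step 5 applies, and p falls below 0.05 from 6 patients upwards. If baseline is left blank, there is no pair.

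**The case against.** The strongest reply is that most of the paragraph is sound. Exercise is ordered by frequency and CTCAE grades are ordered, so a sign test suits them. Presence or absence is binary, so McNemar suits it. HFS at months 6 and 9 against the previous visit is interpretable. All of this stands. A reader might infer that every habit is nominal, or that none of these paired p-values has meaning; the category lists do not support that.

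Napping is unclear only in its middle two options, and a stated order would repair it. That also stands.

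On HFS, a reader might infer that it is not recorded at baseline. The SAP shows only that it is not tabulated there, and the case report form is not available to settle the matter. The general baseline sentence may not have been meant to reach HFS, since the HFS paragraph itself names only months 6 and 9 against the previous visit. Even so, the sentence lists HFS and baseline together without exception, so a programmer following it would run the test.

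The consequences are also limited. The study is described as descriptive. The objectives on habits concern their effect on fatigue and HFS, which is analysed by association tests. The table list names no table for paired tests of habits. FACIT-Fatigue is assigned a paired t-test or Wilcoxon test. Summarising each habit by its most frequent option over 12 weeks should reduce apparent switching, and no document gives switching rates. These points reduce the importance of the error. They do not make a sign test valid for morning, afternoon and night.

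**Conclusion.** Wrong as written, minor, and confined to secondary descriptive analyses. For medication time the prescribed test has no defined result until someone chooses an order, and that choice alone can carry p across 0.05 (0.200 against 0.043 in the moderate example). For napping the same holds only for the two middle options. For HFS and medication time against baseline, the test either cannot be run or is close to automatic once 6 patients contribute.

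The sizes rest on hypothetical tables, a two-sided 0.05 level, at most 95 pairs, and assumed HFS rates. They show what can happen and do not predict this study's results. The documents do not support extending the point to exercise, fatigue grade, HFS at months 6 and 9 against the previous visit, or the primary FACIT-Fatigue analysis.

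**What to change.** In SAP 8.2.3, replace the single sentence on paired tests with an assignment by variable:

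- **Medication time:** Stuart-Maxwell (marginal homogeneity) or Bowker test, between on-treatment visits only, with a pre-stated rule for collapsing sparse categories. Check that the software procedure treats the categories as unordered.
- **Napping:** either state the category order in advance or use the same nominal test.
- **Exercise and CTCAE grades:** keep the sign test or use the Wilcoxon signed-rank test, with the order stated.
- **Binary presence:** keep McNemar.
- **Baseline:** drop the tests of HFS and of medication time against baseline. Report HFS incidence at each visit with its 95% CI. The frequencies are already planned and the SAP already sets a 95% confidence level, so this only makes the interval explicit.

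No new data are needed. The cost is a few lines of SAP text and slightly more programming. The one real drawback is that little-used medication-time categories may leave sparse cells, which is why the collapsing rule should be fixed before the data are seen.
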